- Contra-indication to using AffloVest including lung malignancy, recent rib fractures, radiological evidence of lung cavitation, and recent significant haemoptysis (in the opinion of the investigator)
- History of poor adherence to physiotherapy treatment
- Cognitive or memory problems affecting ability to follow instructions or give informed consent

Recruitment

The planned recruitment target is 30 participants. No strategies for promoting or boosting recruitment are deemed necessary, other than 'in-house' referral from respiratory physicians and physiotherapists working at the Cambridge Centre of Lung Infection, Royal Papworth Hospital.

Section 3. Sample Size and Data analysis

Sample Size:

N = 30.

There are currently no data on which to base an estimation of treatment effect following implementation of high frequency chest wall oscillation, nor what the minimal clinically significant change in CT parameters might be. Thus feasibility data are required to guide the design and power calculation of a future larger study to test treatment efficacy. In these circumstances, we have suggested a sample size of 30 patients, as we anticipate that this will allow sufficiently precise estimation of the size and variability of the treatment effect. Furthermore, if we encounter a drop out rate of 15%, a cohort size of 30 would generate 95% confidence intervals 2.2% and 27.8%.

Statistical Analysis:

To analyse the primary outcome, the CTs will be reviewed by two independent radiologists blinded to the time point for each scan and quantified using the "mucus component" of the modified Brody scoring system. If there is discrepancy on the score for an individual participant at one time point, the two scores will be averaged. After the modified Brody score for each patient is determined we will calculate summary statistics including group mean, standard deviation, standard error and confidence intervals at baseline and after 6 weeks of treatment. Other feasibility measures such as participant dropout rate will also be calculated.

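### Is the protocol's 95% interval of 2.2% to 27.8% for a 15% dropout rate in 30 participants wrong?

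*Protocol*

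**What the plan says.** Section 3 of the protocol, under Sample Size, sets N at 30 because there are no prior data on the effect and no known minimal important change in the CT measures. The reason given for 30 is that "we anticipate that this will allow sufficiently precise estimation of the size and variability of the treatment effect". A further remark then says that "if we encounter a drop out rate of 15%, a cohort size of 30 would generate 95% confidence intervals 2.2% and 27.8" (per cent). The interval method is not named.

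Two other statements in Section 3 bear on how far the figure reaches. Under Sample Size: "Thus feasibility data are required to guide the design and power calculation of a future larger study". Under Statistical Analysis: "Other feasibility measures such as participant dropout rate will also be calculated". Neither attaches a limit, a target or an interval method to the dropout rate.

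**The concern.** The normal approximation for a proportion is weak when events are few, and 15% of 30 is 4.5 expected dropouts. The printed interval is symmetric about 15%, whereas small-sample methods pull the centre up to 18% or 19%. Taken literally, the sentence lets a reader treat dropout rates above about 28% as excluded, when other standard methods would still allow 31% to 33%.

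This is also the only numerical precision statement offered alongside N = 30, dropout is a named feasibility measure, and the study exists to inform a larger trial. Understating the upper limit is the unhelpful direction when allowing for attrition. If the later trial were planned from these limits, or if a go/no-go rule used them, the choice of method could matter.

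**Working it through.** **Inputs.** Dropout rate p = 0.15, cohort n = 30 and a two-sided 95% level, all from the Sample Size paragraph; z = 1.96. The implied count is x = 30 × 0.15 = 4.5, which is not a whole number.

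**The protocol's figure.** Wald: p ± z√(p(1−p)/n).
- √(0.15 × 0.85/30) = √0.00425 = 0.0652
- 1.96 × 0.0652 = 0.1278
- 0.15 ± 0.1278 = 0.0222 to 0.2778, that is 2.2% to 27.8%

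This matches to the rounding. A continuity-corrected Wald interval (0.6% to 29.4%) and a t-based one (1.7% to 28.3%) do not.

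**Alternatives at the same inputs.** For Wilson:
- centre: (0.15 + 3.84/60)/(1 + 3.84/30) = 0.2140/1.128 = 0.1897
- half-width: 1.96 × √(0.00425 + 3.84/3600)/1.128 = 0.1267
- limits: 6.3% to 31.6%

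The Jeffreys limits are the 2.5% and 97.5% points of Beta(5, 26). The exact-type limits are the 2.5% point of Beta(4.5, 26.5) and the 97.5% point of Beta(5.5, 25.5). Since 4.5 is not an attainable count, these two are the formulas evaluated between 4 and 5.

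| Method | Lower | Upper | Width (points) | Upper limit in participants of 30 |
|---|---|---|---|---|
| Wald (as printed) | 2.2% | 27.8% | 25.6 | 8.3 |
| Wilson | 6.3% | 31.6% | 25.3 | 9.5 |
| Agresti-Coull | 5.8% | 32.2% | 26.4 | 9.7 |
| Jeffreys | 5.6% | 30.7% | 25.1 | 9.2 |
| Exact-type | 4.7% | 32.7% | 28.1 | 9.8 |

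All four alternatives lie higher at both ends. They also differ among themselves, by up to 1.6 points at the lower limit (6.3 − 4.7) and 2.0 at the upper (32.7 − 30.7). Half-widths run from 12.5 to 14.0 points, against 12.8 for Wald.

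**Attainable counts.**
- 4/30: Wald 1.2% to 25.5%, Wilson 5.3% to 29.7%, exact 3.8% to 30.7%.
- 5/30: Wald 3.3% to 30.0%, Wilson 7.3% to 33.6%, exact 5.6% to 34.7%.

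Measured from the printed limits, the alternatives lie about 0.9 to 3.1 points higher at 4/30 and 3.4 to 6.9 higher at 5/30. The size of the gap therefore depends on the count and method taken as the reference.

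**What uses the figure.** N = 30 is not solved from the dropout interval; its stated basis is precision of the treatment effect. Section 3 contains no dropout threshold, progression criterion or stopping rule. It says only that the dropout rate will be calculated, so the method for the real interval stays open. Replacing 2.2% and 27.8% by any other row of the table changes no sample size, analysis or decision.

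**The case for a change.** The strongest case for a correction is that the 95% label is not met over much of the relevant range. Exact binomial calculation at n = 30 gives Wald coverage of 94.2% at a true dropout rate of 15%, but about 81% at 10%, 88.3% at 12%, 86.5% at 16% and 91.4% at 18%. Averaged over true rates from 5% to 30% it is 90.7%, against 95.4% for Wilson and 97.5% for exact limits. The misses are lopsided: over that range the Wald interval lies wholly below the true rate 8.2% of the time and wholly above it 1.2%. The tails at the printed limits agree. At a true rate of 27.8%, 4 or fewer dropouts has probability 5.2% and 5 or fewer 12.1%; at 2.2%, 4 or more has probability 0.4%.

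All of this stands, and the near-nominal 94.2% at exactly 15% should not be used as a defence. A statistician analysing the real dropout count would do better with Wilson or exact limits. But this is an argument about how to analyse a future count, which the protocol has not fixed and may properly leave to an analysis plan. It does not show that the printed sentence is miscalculated, contradicts anything else in the protocol, or misleads a decision. The larger trial would be planned from the dropout actually observed, with its own interval, and not from this hypothetical 15%.

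**Conclusion.** The concern does not hold. The printed limits are the correct result of a recognised method applied to the protocol's own inputs. Small-sample methods would place the limits 2.4 to 4.1 points higher at the lower end and 2.9 to 5.0 higher at the upper, about 0.9 to 1.5 participants of 30 at the upper end. The width is essentially unchanged for Wilson and Jeffreys, 0.9 points more for Agresti-Coull and 2.5 points more for exact limits. Every version conveys that 30 participants give only a rough estimate of dropout.

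This rests on two readings of Section 3: that the interval refers to the dropout proportion among all 30 enrolled, which the exact reproduction supports, and that no dropout threshold is tied to it, which holds for the protocol as written. If a later document set a progression rule on an interval limit for dropout, the choice of method would need to be looked at there.

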30 adult subjects (male and female) who have a known diagnosis of bronchiectasis and who attend the Cambridge Centre for Lung Infection (CCLI) at the Royal Papworth Hospital will be recruited.

Subjects will be recruited through convenience sampling and must demonstrate stability during a 2week period prior to enrolment. Stability is defined as no change in medical treatment.

Participants will be asked to use the AffloVest for 30 minutes twice daily (in addition to their standard airway clearance regimen where possible) for six weeks, with clinical review and tests performed at baseline, three and six weeks.

Tests to be performed at baseline, after three and six weeks of treatment with the AffloVest include: computer tomography (CT) at full inspiration and full expiration; spirometry (FEV1 and FVC); and the patient reported outcomes Visual Analogue Scale for ease of sputum clearance (VAS), St George's Respiratory Questionnaire (SGRQ) and Quality of Life–Bronchiectasis (QOL-B).

The CT images will be scored by two independent expert thoracic radiologists using the modified Brody Scoring System which is sensitive and reproducibe.¹² Both radiologists will be blinded to the time point of the CT scans being analysed and if there is disagreement in scores, an average will be taken.

We hypothesize that there will be a reduction in the amount of mucus plugging and an improvement in patient reported outcomes following implementation the AffloVest in adults with bronchiectasis.

Primary Outcome

The primary outcome of this study is to test the feasibility of using computer tomography and the modified Brody score to measure the amount of mucus plugging within the lungs of adults with bronchiectasis at baseline and after six weeks of treatment with the AffloVest. The study outcomes will facilitate the design of a future study to test treatment efficacy.

Secondary Outcome(s)

Secondary outcomes include the full modified Brody score, lung function, quality of life scores and a visual analogue score for ease of sputum expectoration measured at baseline, after 3 weeks of intervention and after 6 weeks of intervention. There will also be a sub-group analysis excluding patients that have a pulmonary exacerbation during the study.

Rationale

Bronchiectasis is a chronic inflammatory suppurative respiratory disease associated with poorer quality of life, increased admissions and increased mortality.^{1,2} The disease is characterised by a

AffloVest Study

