However, to date, there have been no studies of HFCWO in adult patients with bronchiectasis utilising CT to measure the amount of mucus within the lungs before and after implementation of this intervention. This study aims to assess the feasibility of the protocol and to estimate the size and variability of the treatment effect with the AffloVest to facilitate the design of a future study to test treatment efficacy in adults with bronchiectasis.

Schedule of Events

Day -21 to Day -1

• Informed consent and review of inclusion & exclusion criteria

Day 1 – Start of intervention

- CT scan; FEV1 and FVC; PROs (VAS for ease of sputum clearance, SGRQ & QOL-B).
- Participants will be shown how to use the AffloVest and will complete a skills checklist for home use.
- 3 weeks of AffloVest for 30 minutes twice a day (10 minutes each of percussion, vibrations and drainage at an intensity tolerable by each individual participant) in addition to their standard airway clearance regimen (where possible).

Day 21 – Midpoint of intervention

- CT scan; FEV1 and FVC; PROs (VAS for ease of sputum clearance, SGRQ & QOL-B); adherence check.
- 3 further weeks of AffloVest for 30 minutes twice a day (10 minutes each of percussion, vibrations and drainage at an intensity tolerable by each individual participant) in addition to their standard airway clearance regimen (where possible).

Day 42 – End of intervention

 CT scan; FEV1 and FVC; PROs (VAS for ease of sputum clearance, SGRQ & QOL-B), adherence check.

2. Patient Recruitment Criteria

Study Population

Participant number: n = 30

Population group: Adults (males and females) with bronchiectasis who attend the Cambridge Centre for Lung Infection, Royal Papworth Hospital NHS Foundation Trust

Time in study: A total of 63 days from enrolment

Inclusion

- Adult male and females ≥18 years
- Current diagnosis of bronchiectasis (see above definition)
- Productive of sputum on a daily basis
- Clinical stability over a 2-week period prior to enrolment (see above definition)

Exclusion

- Cystic fibrosis
- Severe obstructive airways disease (defined as FEV1 < 25%)
- Predominant lung disease is not bronchiectasis in the opinion of the investigator (e.g. asthma; COPD; pulmonary fibrosis)
- Bronchiectasis in only 1 lobe
- Currently treated non-tuberculous mycobacterial lung disease
- Acute congestive cardiac failure
- Contra-indication or unable to perform HRCT imaging, including pregnancy

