Secondary outcome summary statistics including the full modified Brody score, FEV1, FVC, SGRQ, QOL-B, VAS score and adherence to treatment will be calculated at baseline, after 3 weeks of treatment and after 6 weeks of treatment. Any participants who suffer an exacerbation of their bronchiectasis during the trial will continue in the study and will be included in the analysis of the primary endpoint. However, an additional sub-group analysis will be undertaken excluding this population as a secondary outcome.

Finally, we will also carry out paired t-tests to assess change in CT, lung function and symptom parameters following implementation of the AffloVest. However, this is not the primary aim of this feasibility study and the study may be significantly underpowered to properly address this point. In any case, data generated by the study will inform the design of a larger trial to fully investigate efficacy. A p-value of 0.05 will be interpreted as statistically significant unless otherwise stated.

4. Consent Process and Visit Schedule

Visits

- Subjects will be approached about the study by the CCLI Research team, physiotherapy team or CCLI consultant team at an outpatient appointment, during a day case / inpatient visit or via postal invitation (if known to the service and deemed appropriate for the study). Once seen, and if deemed to be eligible for the study, they will be consented and enrolled.
- Each participant will be assigned a study number; the study numbers will be allocated sequentially starting at 10.
- Participants will then be arranged to undergo first visit testing with treatment and follow up according to the schedule below.
- Visits will be scheduled and performed according to table 1.
- Trial specific procedures *versus* routine procedures are detailed in table 2. The trial specific
 procedures will only be performed after written informed consent has been obtained.

Visit Number	Screening	Visit 1	Visit 2	Visit 3
Time interval of Visit	Day -21 to day -1	Day 1	Day 21	Day 42
Informed consent	X			
Review of inclusion & exclusion criteria	X	X		
Medical history and examination		X	X	X
Size for AffloVest	X			
Fit AffloVest, teach how to use it, check tolerance of settings		X		
AffloVest skills checklist of participant competency		X	X	X
AffloVest adherence tracking			X	X
Spirometry (FEV ₁ and FVC)		X	X	X
Pregnancy test if appropriate (urine dipstick)		X	X	X
Patient reported outcomes (VAS, SGRQ & QOL-B)		X	X	X
CT scan		X	X	X

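### Does leaving the week-3 mucus score and the SD of within-person change off the list of outputs undermine the study's aim?

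*Protocol*

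**What the plan says.** All references are to the protocol. Its Rationale sets the aim "to estimate the size and variability of the treatment effect with the AffloVest", and Sample Size in Section 3 adds that "feasibility data are required to guide the design and power calculation of a future larger study to test treatment efficacy".

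The Primary Outcome in Section 1 concerns mucus plugging at baseline and after six weeks. Statistical Analysis in Section 3 follows it: the mucus component is scored by two blinded radiologists, and summary statistics are given, including the mean, SD, standard error and "confidence intervals at baseline and after 6 weeks of treatment".

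The secondary measures are treated more fully. Section 1 says "Secondary outcomes include the full modified Brody score", and Section 3 begins the matching analysis with "Secondary outcome summary statistics including the full modified Brody score"; both give baseline, week 3 and week 6. The visit schedule in Section 4 has a CT at Day 1, Day 21 and Day 42.

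Change is covered by one sentence, which plans "paired t-tests to assess change in CT, lung function and symptom parameters following implementation of the AffloVest". The protocol adds that this is not the primary aim and that power may be low.

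**The concern.** Two things look out of order. First, the main measure has fewer listed visits than a secondary one taken from the same images, so the Day 21 mucus score has no listed summary. Second, the variability of a before-after effect is the SD of within-person change. Two visit SDs do not give it, because it also depends on the correlation between visits. The sentence on paired tests names neither the CT score nor the pair of visits, and a p-value alone yields no SD.

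If the study reported only the listed visit summaries, the next trial's designers would lack the figure on which their sample size depends most. They would also not know how much of any change in mucus was already present at three weeks.

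**Working it through.** **The protocol's one computed figure.** Sample Size gives a 95% interval of 2.2% to 27.8% for 15% dropout in 30 participants. The normal approximation gives 0.15 ± 1.96 × √(0.15 × 0.85 / 30) = 0.15 ± 0.128, or 2.2% to 27.8%. It reproduces. The protocol gives no figure for the mucus score or its change, so the inputs below are assumptions.

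**Do visit SDs determine the SD of change?** Take equal visit SDs of 1 and correlation r, so that SD of change = √(2(1 − r)). For a later two-arm trial assume a difference of 0.3 SD, 80% power and two-sided 5%. Sample sizes on change scores use exact t power. The baseline-adjusted ones use 2 × 7.849 × (1 − r²) / 0.09.

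| r | SD of change | n per arm, change scores | n per arm, baseline-adjusted |
|---|---|---|---|
| 0.4 | 1.10 | 211 | 146.5 |
| 0.5 | 1.00 | 176 | 130.8 |
| 0.6 | 0.89 | 141 | 111.6 |
| 0.7 | 0.77 | 106 | 89.0 |
| 0.8 | 0.63 | 71 | 62.8 |

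The visit summaries cannot tell these rows apart; the range on change scores is 211/71 = 3.0-fold. The concern is right to this extent.

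**Does the plan produce the SD of change elsewhere?** A paired t-test is t = mean difference / (SD of change / √n). The mean and SD of the differences are its ingredients, and SD of change = |mean difference| × √n / |t|. The protocol has two CT scores, the mucus component and the full Brody score. Read naturally, CT parameters include the one used for the primary outcome, and the visits at which that outcome is defined supply the pair.

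**How much would reporting it settle?** At 15% dropout, 0.15 × 30 = 4.5 are lost, leaving 25 or 26 pairs. The chi-square 95% interval for an SD from 26 pairs is 0.784 to 1.380 times the estimate. Sample size goes with the square of the SD, so the later trial's n has a range of (1.380 / 0.784)² = 3.1-fold.

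**What would week 3 add?** With all 30 scans, the standard error of the week-3 mucus change is 0.632/√30 = 0.12 to 1.095/√30 = 0.20 visit SDs. The 95% half-width is 0.373 times the SD of change, or 0.24 to 0.41. Against an assumed six-week change of 0.30 SD, that is too wide to say what share is present at mid-treatment.

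**The case for a change.** The strongest case for a change is that the protocol itself names the statistics and visits, and the named set does not deliver its own aim. On that view a later plan that added the SD of change would be repairing a poor list. The repair needs only wording: the Day 21 scans are already taken and scored by two radiologists, and the mucus component is part of the full score planned for that visit.

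Part of this stands. Neither the week-3 mucus summary nor the SD of change is named, the paired tests are loosely specified, and a report giving only p-values would serve the next trial badly. The estimated SD would also be worth having despite its wide interval, since it gives a centre that an assumed range of correlations does not.

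But the text excludes none of this. The primary sentence fixes the visits, not the statistics; its list is introduced as examples, as are the secondary lists. Reporting baseline and week 6 for an outcome defined at those visits is consistent, and summarising secondary measures more often is a design choice. Treatment length for the next trial is not a stated objective.

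A repeated-measures model using all three scans would not alter the balance. In simulations with assumed correlations of 0.6 to 0.7 and 15% dropout, its standard error ran from 3% lower to 2% higher than that of the paired completers' change. The bias it removes was absent when dropout was unrelated to week-3 change, about 0.01 to 0.03 SD when dropout was symptom-driven, and up to about 0.09 SD under strong selection, against a standard error of about 0.175 SD. Participants who exacerbate "will continue in the study and will be included in the analysis of the primary endpoint", which closes one obvious route to such selection.

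**Conclusion.** No change is called for. The description of the text is accurate, but following the plan as written gives no wrong result. The primary summary agrees with the primary outcome, and the SD of within-person change comes out of an analysis already planned on data already collected. What is missing is a listing of outputs, which protocols commonly leave to a statistical analysis plan. An analyst working to the stated aim would report the mean and SD of the mucus change beside the paired test and could tabulate Day 21 without any amendment.

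The size of the issue rests wholly on assumed inputs: equal visit SDs, correlations of 0.4 to 0.8 and a 0.3 SD difference in a two-arm successor. On these, not knowing the SD of change leaves a 3.0-fold range in the later sample size, and an estimate from 26 pairs still carries about a 3.1-fold 95% range. The conclusion also depends on the paired tests covering the mucus component at baseline and week 6, which is the natural reading of the text.

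### For the week-6 change, the paired t-tests leave out anyone lost after Day 21 although their week-3 data are held; if loss is related to early worsening, the estimate may be too favourable

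*Protocol*

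**What the plan says.** The method for change is fixed in the protocol, Section 3, Statistical Analysis: "we will also carry out paired t-tests to assess change in CT, lung function and symptom parameters". Neither the visit nor the handling of unpaired values is stated. The threshold follows: "A p-value of 0.05 will be interpreted as statistically significant unless otherwise stated". The protocol also limits the role of these tests: "this is not the primary aim of this feasibility study and the study may be significantly underpowered to properly address this point".

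Study Design in Section 1 sets three measurement points: "Tests to be performed at baseline, after three and six weeks of treatment with the AffloVest include: computer tomography (CT"), with spirometry and the patient-reported outcomes in the same list. The Schedule of Events and Table 1 repeat this for Day 21. In the analysis text, week-3 values appear explicitly only in the secondary summary statistics. The primary summaries of the mucus component are at baseline and week 6.

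On loss, Sample Size says "if we encounter a drop out rate of 15%, a cohort size of 30 would generate 95% confidence intervals 2.2% and 27.8" (per cent). The dropout rate is itself reported as a feasibility measure. Participants with an exacerbation continue and stay in the primary analysis. Under Informed Consent Procedure, anyone may withdraw at any time.

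**The concern.** A paired t-test needs both values. Someone who attends Day 21 and then leaves has had two of the three planned CT scans, and the second may show how they were responding, yet they drop out of the week-6 comparison entirely. If people who are doing worse at week 3 are more likely to leave, the remaining pairs give too favourable a change. There is no control arm in which a similar loss could offset this.

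The estimate matters more than the p-value. The study is meant to supply the size and variability of the treatment effect for an efficacy trial, and the choice of N rests on that: "we have suggested a sample size of 30 patients, as we anticipate that this will allow sufficiently precise estimation". Conceding low power does not deal with bias in the estimate.

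**Working it through.** **1. The protocol's own figure.** Inputs from Sample Size: p = 0.15, n = 30. Wald interval: 0.15 ± 1.96 × √(0.15 × 0.85 / 30) = 0.15 ± 0.128, that is 2.2% to 27.8%. This matches. It is an interval for the dropout rate; N is not inflated for loss.

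**2. Pairs left.** At 15%, 30 × 0.85 = 25.5 pairs remain. At the interval's ends, 30 × 0.978 = 29.3 and 30 × 0.722 = 21.7. The 95% CI half-width for a mean change, in SDs of change, is 0.373 with 30 pairs, 0.404 with 26 and 0.413 with 25. The loss of precision is modest; the question is bias.

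**3. Bias in general.** Completers' mean minus everyone's mean = dropout proportion × (completers' mean change − dropouts' mean change). At 15%, if dropouts do 0, 0.25, 0.5 or 1 SD of change worse, the bias is 0, 0.04, 0.08 or 0.15 SD of change.

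**4. Dropout driven by the week-3 change.** The protocol gives no SD, correlation or dropout mechanism, so these are assumptions: true change 0, equal SDs, the same correlation r between any two visits, and 15% lost after week 3 with log-odds rising by a given slope per SD of week-3 worsening.

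- SD of change = √(2(1 − r)): 1.00 baseline SD at r = 0.5 and 0.775 at r = 0.7.
- Correlation of the week-3 and week-6 changes = (1 − r) / (2(1 − r)) = 0.5.
- Slope 0.5 (odds ratio e^0.5 = 1.6): large-sample bias 0.035 SD of change, so 0.035 × 1.00 = 0.035 and 0.035 × 0.775 = 0.027 baseline SD.
- Slope 1.5 (odds ratio e^1.5 = 4.5), simulated at n = 30 and shown in the table.

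| r | Dropout | Complete pairs | Likelihood analysis, all visits |
|---|---|---|---|
| 0.5 | 15% | −0.089 | 0.001 |
| 0.7 | 15% | −0.070 (SE 0.151) | −0.001 (SE 0.154) |
| 0.7 | 27.8% | −0.120 | −0.002 |

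Negative means spurious improvement, in baseline SDs. At r = 0.7 and 15% the bias is 0.070 / 0.151 = 0.46 of a standard error at slope 1.5, and 0.027 / 0.151 = 0.18 at slope 0.5. With dropout unrelated to outcome and a true change of −0.40, the two analyses give −0.403 and −0.402.

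**5. The primary week-6 mean and SD.** These also rest on whoever attends week 6, but the sizes above do not carry over. In the equal-correlation model the covariance of the week-6 value with the week-3 change is r − r = 0. The week-6 mean and SD of completers are then unaffected, and the bias in the paired change comes through completers' higher baselines. They do shift if week 6 correlates more with week 3 than with baseline, or if leaving depends on the week-3 level itself. Both are plausible; the documents settle neither.

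**The case against.** A reader might infer that the week-6 result describes only those who did well enough to stay. The documents do not support that. They give no reasons for leaving, and both the existence and the direction of any bias are assumptions. One obvious outcome-related route is partly closed, because participants with exacerbations continue and are analysed. Vest intensity is set to individual tolerance, and a history of poor adherence is an exclusion. This stands.

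A reader might also take 15% as an allowance built into the design and 27.8% as an expected loss. The first is a conditional illustration of precision and the second is the upper limit of that illustration. This stands too.

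The t-test sentence names no visit. A baseline-to-week-3 test would include these participants, and their week-3 secondary outcomes are summarised, so it would be wrong to say that the study throws the data away. The point is confined to the week-6 contrast.

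For CT the mechanism is weaker. Nothing says participants learn their score. If leaving depends on symptoms correlated 0.3 to 0.5 with CT (an assumption), the bias at 15% and slope 1.5 is only 0.02 to 0.03 SD.

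Finally, the tests are declared secondary and possibly underpowered, and missing-data rules often sit in an SAP, which is not at hand. That lowers the weight of the point but does not remove it. The protocol names a method, that method decides who is analysed, and the estimated change is an obvious planning input even if the p-value is not.

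**Conclusion.** The point holds as a possible bias and a worthwhile improvement, not as a demonstrated error. For the week-6 change the named method is a complete-pair analysis that makes no use of week-3 data from later dropouts. At 15% dropout and correlations of 0.5 to 0.7, the change is too favourable by about 0.03 baseline SD if loss depends weakly on the week-3 change and by 0.07 to 0.09 if it depends strongly. It is unbiased if loss is unrelated to outcome, and the sign would reverse if those who improve are the ones who leave. All of this assumes that the loss falls after week 3. The primary week-6 mean and SD rest on the same participants and may also be affected, by an amount these figures do not give.

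**What to change.** In Statistical Analysis, or in the SAP, estimate week-3 and week-6 change with 95% CIs from one repeated-measures linear mixed model per parameter: visit as a three-level factor, unstructured within-participant covariance, REML with a small-sample degrees-of-freedom correction such as Kenward-Roger, and all observed visits. Report the model-based week-6 mean of the mucus score beside the primary summary statistics; otherwise the primary output stays on completers alone. The week-3 mucus component should be available, since the full modified Brody score is already planned at that visit. Keep the complete-pair t-test as a sensitivity analysis, and name its visit.

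The cost is wording and slightly more analysis, with no new data. Precision is nearly unchanged (SE 0.154 against 0.151 in the r = 0.7, 15% case). The model relies on data being missing at random. It does not repair loss before week 3 that depends on change nobody measured.

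### Seven measures, possibly each at two follow-up visits, are to be tested and labelled statistically significant at 0.05, with no designated test and no exploratory label (minor)

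*Protocol*

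**What the plan says.** All of the relevant text is in Section 3 of the protocol, under Statistical Analysis.

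- **Tests planned:** "we will also carry out paired t-tests to assess change in CT, lung function and symptom parameters following implementation of the AffloVest". Neither the number of tests nor the visits compared are given.
- **Reading rule:** "A p-value of 0.05 will be interpreted as statistically significant unless otherwise stated". Nothing elsewhere in the protocol states otherwise.
- **Measures:** the primary CT measure is the mucus component of the modified Brody score. The secondary list reads "Secondary outcome summary statistics including the full modified Brody score, FEV1, FVC, SGRQ, QOL-B, VAS score and adherence to treatment".
- **Time points:** the secondary summaries "will be calculated at baseline, after 3 weeks of treatment and after 6 weeks of treatment". The primary measure has summary statistics that include "confidence intervals at baseline and after 6 weeks of treatment". Both sentences concern summary statistics, not the t-tests.
- **Caveats:** the protocol says that testing is not the main purpose of the study, that "the study may be significantly underpowered to properly address this point", and that a larger trial will investigate efficacy.
- **Exacerbations:** "an additional sub-group analysis will be undertaken excluding this population as a secondary outcome". No t-tests are specified for that analysis.

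**The concern.** The protocol does more than leave multiplicity unmentioned. It states a decision rule under which every paired t-test with p below 0.05 earns the label statistically significant. The power caveat warns that a real change may be missed. It does not limit what may be said when a test crosses the threshold.

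The study hypothesis in Section 1 is directional and covers both mucus plugging and patient-reported outcomes, so one nominal success among several measures could be read as support for it. Section 3 also says that the data will inform the design of a larger trial. A chance finding could therefore be given too much weight when that trial is designed. The protocol does not itself tie the choice of endpoint to a p-value, so this is a risk and not a stated plan.

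**Working it through.** **Plan's own figure.** The protocol gives no overall error rate and no number of tests, so there is no figure on this point to reproduce.

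**Inputs from the protocol**

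- Level per test: 0.05. Sidedness is not stated; two-sided is assumed.
- Measures that can be tested as change from baseline: mucus component (1) plus full Brody, FEV1, FVC, SGRQ, QOL-B and VAS (6), which makes 7. Adherence has no baseline value and is left out.
- Participants: 30, in one group.
- Follow-up visits: Day 21 and Day 42, with all seven measures obtainable at both (Schedule of Events; visit schedule in Section 4).

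**Input not in the protocol:** the correlation between test statistics. It is assumed to lie between 0 and 0.7.

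**Number of tests**

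- Baseline to week 6 only: 7 × 1 = 7.
- Following the summary time points: 6 × 2 + 1 = 13, because the mucus component is summarised only at baseline and week 6.
- Both visits for every measure: 7 × 2 = 14.

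**Independent tests, no true change.** The chance of at least one p < 0.05 among k tests is 1 − 0.95^k:

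- k = 7: 1 − 0.95^7 = 0.302
- k = 13: 1 − 0.95^13 = 0.487
- k = 14: 1 − 0.95^14 = 0.512

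For a false result in the favourable direction only, each test contributes 0.025, so the chance is 1 − 0.975^k:

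- k = 7: 1 − 0.975^7 = 0.162
- k = 14: 1 − 0.975^14 = 0.298

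**Correlated tests.** These were simulated: 30 pairs, normally distributed changes, two-sided paired t-tests, one common correlation, 40,000 runs. Outcomes are oriented so that improvement is positive. The zero-correlation row gives the exact values above.

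| Correlation | 7 tests, either direction | 14 tests, either direction | 7 tests, favourable | 14 tests, favourable |
|---|---|---|---|---|
| 0 | 30.2% | 51.2% | 16.2% | 29.8% |
| 0.3 | 27.3% | 44.4% | 14.2% | 22.7% |
| 0.5 | 23.4% | 35.4% | 11.8% | 17.8% |
| 0.7 | 18.3% | 25.5% | 8.9% | 12.8% |

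With 14 tests and separate correlations of 0.5 between outcomes and 0.7 between visits, the either-direction figure is 36.1%. Using 26 pairs in place of 30, roughly what remains after the 15% dropout that the protocol considers (30 × 0.85 = 25.5), leaves the tabulated figures essentially unchanged.

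**Expected number of false significant results.** This does not depend on correlation: 7 × 0.05 = 0.35, or 14 × 0.05 = 0.70.

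**The case against.** The strongest reply is that the tests are already subordinate. The primary analysis is descriptive, the protocol says that testing is not the main aim, efficacy is deferred to a larger trial, and no go/no-go decision depends on a p-value. Unadjusted secondary tests in a single-group feasibility study of 30 are not in themselves an error. A list of tests or a multiplicity rule may sit in a statistical analysis plan that is not shown, and the protocol's allowance for exceptions to the threshold leaves room for one.

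Most of this stands, and it is why the point is minor. It does not remove the point, because the protocol itself fixes the 0.05 label for every test, and none of its caveats limits what may be claimed once that label applies.

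A reader might also infer more than the text supports:

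- **That there are at least 14 tests, with a false-positive chance of 36% to 51%.** Fourteen is the upper count for these seven measures. Seven tests also satisfy the wording, and the 36% floor needs both 14 tests and a moderate correlation that the protocol does not give.
- **That a false significant benefit is likely.** In the favourable direction the chance is at most about 30% over the range examined.
- **That the exacerbation-free analysis doubles the count to 28.** No t-tests are specified for it, so that figure has no basis in the document.
- **That the power warning is the only caveat.** The same paragraph also says that testing is not the main aim and leaves efficacy to a later trial.

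**Conclusion.** The point holds at minor severity. The protocol applies a significance label at 0.05 to each of 7 to 14 paired t-tests without designating one or calling them exploratory.

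With no true change, the chance of at least one false significant result is about 30% to 51% if the tests are independent and about 18% to 26% at a correlation of 0.7. The chance of one in the favourable direction is about 9% to 30% over the same range. These figures rest on the count of seven measures, on one or two visits per measure, on two-sided tests, and on assumed correlations. Even the lowest either-direction figure is more than three times the nominal 5% (18.3 / 5 = 3.7).

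The risk is substantial rather than probable. It concerns how secondary results are described, not the primary feasibility outcome.

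**What to change.** Change the closing paragraph of Statistical Analysis in Section 3 to say that:

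1. for each measure, the paired change from baseline will be reported with its SD and 95% confidence interval;
2. any p-values are unadjusted and descriptive and will not be used to claim benefit;
3. if one test is wanted, the baseline-to-week-6 change in the mucus component, in all participants, is the only one read against 0.05.

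The first item also serves the stated aim better than confidence intervals at each visit. The size and variability of the effect are properties of the paired change, and its SD cannot be recovered from the two visit SDs without their correlation.

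Removing the allowance for exceptions to the threshold is optional.

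The cost is a few sentences, with no extra participants, scans or visits. The downside is that secondary changes can no longer be called statistically significant.
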